#### **8.3** Description of the Analyses

In presenting data from this trial, continuous data will be summarized in tables listing the mean, standard deviation or standard error, median, and number of subjects in a group. Categorical data will be summarized in tables listing the frequency and the percentage of subjects in a group. These summaries will be presented separately for subjects on the two treatment arms.

# 8.3.1 Safety Analysis

All safety analyses will be performed using the Safety Population.

AEs including changes in laboratory values will be graded according to the National Cancer Institute's *Common Terminology Criteria for Adverse Events (CTCAE) Version 4.0* (http://ctep.cancer.gov/reporting/ctc.html). The frequency of AEs will be summarized by system organ class, preferred term, severity (grade), and relationship to study treatment. Relationship to study treatment will be categorized as either treatment related (possibly, probably, or definitely related to study medication) or unrelated (unlikely related or unrelated). Similar analyses will be performed for SAEs. To account for differential duration of study participation among subjects, the summaries will include the event rate (i.e. number of events per person-time) in addition to the number and percent of events and subjects experiencing events.

For each key safety endpoint defined in Section 3.3.2, *Secondary Safety Endpoints* the proportion of subjects experiencing at least one event in each treatment group will be reported and the treatment groups compared based on Fisher's Exact Test. In addition, event rates in the two arms will be compared using Poisson regression.

Laboratory parameters will be summarized both overall and by treatment group using appropriate descriptive statistics. For each lab parameter, the number and percent of subjects that have an increase, decrease, or no change from baseline to Week 60 will be displayed for each treatment group and pooled across treatment arms. For parameters with an explicit NCI-CTCAE grading criterion, change from baseline will be indicated by a change in grade. For

parameters that do not have an explicit NCI-CTCAE, observed values will be categorized as 'high' (defined as >ULN) and 'normal' (defined as  $\leq$  ULN). Then, a change from baseline will be indicated as a change in category

[figure not shown]
All safety comparisons and associated p-values are considered exploratory, not as formal tests of hypothesis. As such, no adjustments will be made for multiple comparisons and all p-values must be interpreted cautiously.

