#### 8.5.6 **Changes to the Statistical Analysis Plan**

A detailed description of the planned analyses will be provided in a SAP to be completed and signed off prior to the completion of the trial. Major changes from this protocol will be noted in the SAP. If there is sufficient reason to do so, revised plans may be issued during the course of the study. Changes to the SAP that are made subsequent to database lock will be documented in the clinical study report.

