Data will be obtained from a variety of sources including, but not limited to laboratory notebooks, automated instrument output files, and clinical subject charts. Data from these source materials will be transmitted to the SACCC via one of two mechanisms. Data collected electronically at central laboratories will be transferred electronically directly from the laboratory to the SACCC using standard secure data transfer procedures. Data collected at the clinical sites will be transmitted to the SACCC using an internet-based remote data entry system. Clinical site personnel use an internet browser to key data into e-CRFs; each CRF page is submitted to the clinical database electronically as the page is completed. Univariate data validation tests are performed as the data are keyed. The clinical database is backed up nightly; backup tapes are saved in a secure, off-site location. At any time, authorized site personnel may log in to the remote data entry system, review and correct previously entered data, or key additional data. The data will be further validated per the study data validation plan via a series of computerized and manual edit checks, and all relevant data queries will be raised and resolved on an ongoing basis. Complete, clean data will be frozen to prevent further inadvertent modifications. All discrepancies will be reviewed and any resulting queries will be resolved with the investigators and amended in the database. All elements of data entry (i.e., time, date, verbatim text, and the person performing the data entry) will be recorded in an electronic audit trail to allow all data changes in the database to be monitored and maintained in accordance with federal regulations.

The SACCC will periodically visit the participating clinical sites and audit the source documents in order to validate the data in the SACCC central database. Data will be provided using the subject's screening or enrollment number, the SACCC will not collect personally identifying information such as the subject's name or social security number. Subjects will provide demographic information such as race, ethnicity, and birth date.

Data collected by the SACCC will be held in the strictest confidence, and are protected from access that could reveal personally identifying information about any subject in the trial.

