# 8.5. Clinical Laboratory Evaluation

Clinical laboratory measurements include serum chemistry, urinalysis, and hematology. Results will be converted to standardized units where possible. Chemistry and hematology panels are run by a central lab; as such, normal ranges will come from the central lab.

Laboratory data will be plotted to show patterns over time. Summary statistics including 25th percentile, median, and 75th percentile will be plotted for each visit by treatment group. Lines connecting individual subject results from subjects with grade 2 or higher values will be overlaid on each figure. For lab results that are not gradable, results from subjects with values outside of 2 \*ULN or 0.5\*LLN will be overlaid. Tests with qualitative results (such as "present" or "positive") will not be plotted.

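### No table counts central-laboratory toxicity grades by arm: the protocol's table looks only at baseline and Week 60, and the SAP leaves it out without saying so

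*Protocol*

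**What the plan says.** Protocol 8.3.1 makes two provisions for laboratory data. The first is general: "Laboratory parameters will be summarized both overall and by treatment group using appropriate descriptive statistics". The second is the only one that counts subjects: for each parameter, "the number and percent of subjects that have an increase, decrease, or no change from baseline to Week 60 will be displayed", by arm and pooled. Change means a change in CTCAE grade where a grading criterion exists. Otherwise values are split at the upper limit of normal into high and normal.

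SAP 8.5 does not contain that table. It says "Laboratory data will be plotted to show patterns over time", and specifies: "Summary statistics including 25th percentile, median, and 75th percentile will be plotted for each visit by treatment group". It adds: "Lines connecting individual subject results from subjects with grade 2 or higher values will be overlaid on each figure". For tests that cannot be graded, the overlay shows subjects with values beyond twice the upper limit or below half the lower limit of normal. SAP 8.1 provides listings of all safety measurements.

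On the data source, SAP 8.5 says "Chemistry and hematology panels are run by a central lab", and Protocol Section 10 says "Data collected electronically at central laboratories will be transferred electronically directly from the laboratory to the SACCC". On departures from the protocol, Protocol 8.5.6 says "Major changes from this protocol will be noted in the SAP". SAP Section 12 lists four changes, none about laboratory data.

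**The concern.** Describing toxicity on and off MMF is a secondary safety objective (Protocol 2.2.2). The control arm is there partly to allow that comparison (1.5.4), and hematological derangement is one of the harms to be weighed against flare risk (8.3.2.1). A comparison of two time points suits a lasting difference between arms. It does not suit toxicity that comes and goes, and Protocol 5.4.2 anticipates exactly that course: study drug is held, counts are repeated weekly, and drug may resume on recovery.

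The trial is open-label. If toxicity counts come only from events that unblinded investigators enter, a difference between arms in how completely laboratory changes are recorded could be mistaken for a difference in toxicity. The central laboratory's values reach the coordinating center by a separate route and could serve as a check, but neither document plans a count from them.

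**Working it through.** No sample size, power or event figure is at issue, so the check is a count of visits and a comparison of sections.

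**Visits available and used** (Protocol 6.4 and Table 6.1)
- Hematology is drawn at Weeks 4, 8, 12, 16, 20, 24, 32, 40, 48 and 60, which is 10 scheduled post-baseline visits. The protocol table uses Week 60 only and leaves out 10 − 1 = 9.
- The chemistry panel is drawn at Weeks 12, 24, 32, 40, 48 and 60, which is 6. The table uses 1 and leaves out 6 − 1 = 5.
- Creatinine is also run alone at Weeks 4, 8, 16 and 20, giving 6 + 4 = 10, of which the table uses 1.

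**What the protocol table does with a transient abnormality.** Take a subject with normal neutrophils at Day 0, Grade 3 neutropenia at Week 24, and normal neutrophils again from Week 32. The grade at Week 60 equals the grade at baseline, so the subject is classed as no change. In the withdrawal arm Week 60 comes 60 − 12 = 48 weeks after the end of the taper.

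**What it does with low ungraded values.** Everything at or below the upper limit is normal, so a fall below the lower limit produces no change of category.

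**What replaces it.**

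| Source | Timing | Output | Count by arm from central-laboratory values? |
|---|---|---|---|
| Protocol 8.3.1 table | Baseline and Week 60 | Number and percent | Yes, at Week 60 only |
| SAP 8.5 | Every visit | Quartile plots with overlaid lines | No |
| SAP 8.1 | Every assessment | Listings | No |
| SAP 8.3 and 8.3.1 | Whole study | Adverse-event counts, rates and tests | No; uses adverse-event case report form entries |

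**Is the omission recorded?** The four items in SAP Section 12 concern SAP 7.2, 7.3.3, 7.3.6 and 11.1. Items on laboratory analysis: 0 of 4.

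**What the adverse-event route covers.** Protocol 7.4.1 makes a rise in CTCAE grade an adverse event, measured from Day 0 or from the last post-baseline value that met no grading criterion. Protocol 7.3.4 has the investigator record Grade 2 and above. SAP 8.3.1 compares the Grade 3-5 and hematological endpoints by Fisher's exact test and Poisson regression. The neutropenia in the example should therefore appear there. Outside this route are Grade 1 changes, which are not recorded, and any rise that a site does not enter. The SAP's hematological endpoint is defined by system organ class alone. Infections and malignancies each add a yes/no question from the case report form.

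**Baseline for chemistry.** The panel is drawn at screening but not on Day 0, where only creatinine is run. Neither Protocol 8.3.1 nor SAP 8.5 says which visit is baseline for parameters such as transaminases.

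**The case against.** The strongest reply is that the adverse-event rules already do this work. For gradable parameters, adverse-event status follows from a change in grade rather than from opinion. The rule applies visit by visit, and the events are tabulated by arm, by maximum severity and as rates. The coordinating center receives the laboratory values and is responsible for checking completeness and consistency (Protocol Section 10). This stands in large part. A reader might infer that transient toxicity is never counted by arm; the documents do not support that. What remains is that the counts depend on entry by unblinded sites, and no planned tabulation would show whether entry was equally complete in both arms. The documents contain no evidence that it is unequal.

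Four other readings go too far.
- *Low values cannot be seen under the SAP.* They can: its plots overlay ungraded values below half the lower limit, and graded values at Grade 2 or higher. The weakness belongs to the protocol's high/normal split.
- *Laboratory grades are the only safety measure free of open-label reporting.* All-cause mortality is also a safety endpoint.
- *Most transient toxicity is missed, by some stated percentage.* Any such figure needs assumed onset times and durations that the documents do not give. It would also describe a table that the SAP does not run.
- *The SAP broke the protocol's rule on recording changes.* That rule covers major changes only, and the sponsor can fairly call one descriptive, exploratory table minor. The SAP omits the table without expressly withdrawing it.

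It is also fair to say that Week 60, with 48 weeks off MMF in one arm, is a contrast of interest in its own right. It answers a different question from how many subjects ever had toxicity.

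**Conclusion.** The point holds as a limited reporting gap. The one by-arm laboratory count in the protocol ignores 9 of 10 scheduled post-baseline hematology visits and 5 of 6 chemistry panels. The SAP leaves that count out without explanation and puts no other count of central-laboratory grades in its place. Changes of Grade 2 or higher should still reach the adverse-event tables, so the loss is an arm-level count that does not depend on unblinded entry, together with Grade 1 shifts. The size of any resulting bias cannot be derived from the documents. No endpoint, test or sample-size figure changes, and the primary analysis is untouched. This is a worthwhile, inexpensive improvement rather than a defect that threatens the trial's conclusions. The conclusion assumes that plots and listings are not read as counts, and that the SAP's silence on the table means it will not be produced.

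**What to change.** In SAP 8.5 add one table, by arm in the safety population, of baseline CTCAE grade against worst post-baseline grade, derived from the central-laboratory data. Use low, normal and high for parameters without a grade. State which visit is baseline for chemistry parameters not drawn on Day 0. Add an item to SAP Section 12 saying that this table replaces the baseline-to-Week-60 table. A second version limited to Weeks 12-60, after the taper, is optional.

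The cost is one standard table from data already collected, and the Grade 2 overlays in SAP 8.5 already require laboratory values to be graded. The drawback is that a worst-value table picks up some isolated abnormal results; the planned by-visit plots give the context for reading them.

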# 8.3.2 Analysis of Disease Activity Endpoints

#### 8.3.2.1 **Primary Endpoint Analysis**

The hope is that this study will provide physicians with some rationale for medical decision making. It is important to note that in practice the decision to withdraw from MMF is multifactorial; one has to weigh the increased risk of disease reactivation against decreased risk of lymphoproliferative disease, hematological derangements, and infections as well as the impact of chronic medication use on quality of life and plans for pregnancy. How the risks and benefits should be weighed is highly individual. For example, for one patient, an acceptable increase in risk with MMF withdrawal might be 0.20, but for another, it might be 0.05, where risk is the probability of disease reactivation on a 0 to 1 scale. Acceptable risk varies according to physician and patient circumstances and preferences, so a pre-specified margin of non-inferiority cannot be defined. Hence, a study designed to test a non-inferiority hypothesis with a single pre-specified risk margin that may or may not be relevant for any particular patient would have limited utility. As such, the planned analyses for this study are designed to maximize the information available for medical decision making.

The first step will be to report effect estimates and 95% confidence intervals for the risk of disease reactivation by Week 60 in each arm as well as the estimated risk difference (i.e. risk\_MMFwithdrawal - risk\_MMF maintenance), which we assume will be a positive increase in risk with MMF withdrawal. Next, to aid physicians and patients in making decisions based on individualized assessments of acceptable risk, the observed risk estimates will be used to compute the "% Confidence that the true increase is  $\leq a$ " as a function of values for the "Acceptable increase in risk with withdrawal of MMF (a)". This information can be plotted with values for "Acceptable increase in risk with withdrawal of MMF (a)" on the x axis and estimates for "% Confidence that the true increase is  $\leq a$ " on the y axis. Our study will generate a single curve based on the observed risk estimates for the two arms. Figure 8.1 shows examples of what this plot might look like given a few possible scenarios for the observed risk estimates. Physicians with their patients could decide on an acceptable level of increased risk (a) then read from the plot the % confidence that this selected value of a would not be exceeded with withdrawal of MMF. Depending on the level of confidence, they may or may not decide to withdraw MMF.

# Figure 8.1

The motivation for the curve in Figure 8.1 comes from the test of non-inferiority with the following hypotheses:

*H*0: the increase in risk with withdrawal of MMF (T)  $\ge a$ , and *H*A: the increase in risk with withdrawal of MMF (T) < a, where a is some value for the acceptable increase in risk.

The H0 hypothesis would be rejected in favor of HA if the upper  $(1-\alpha)$  % confident limit about the estimated risk difference (i.e. risk\_MMFwithdrawal - risk\_MMF maintenance) is less than **a**. Then, we could conclude that **T** < **a** with  $(1-\alpha)$ % confidence. Physicians and patients who are comfortable with both a risk increase of no more than **a** and a confidence level of  $(1-\alpha)$ % could conclude that withdrawal from MMF is "not unacceptably worse" than maintenance on MMF.

Recognizing that the appropriate value of a will be highly variable among physicians and patients, a single hypothesis is not defined for this study. Alternatively the upper 1-sided (1- $\alpha$ )% confidence limit (UCL) for the observed risk difference will be computed for values of  $\alpha$  ranging from 0.01 to 0.99. Note that for a given value of  $\alpha$ , the computed UCL equals the value of a, at which a null hypothesis could be rejected with a Type I error rate of  $\alpha$ . Results of these computations will be tabulated and plotted as shown in Figure 8.1.

These analyses will be completed on the mITT population.

# 8.3.2.2 Secondary Analyses

All secondary analyses will be conducted in an exploratory fashion with p-values and confidence intervals presented as descriptive statistics with no adjustments for multiple comparisons. Interval estimates will be generated at the 95% confidence level. Analyses will be conducted on the mITT population and the per protocol population.

Analyses described for the primary analysis of the primary endpoint will be repeated using the per protocol population.

In addition, analysis will be conducted in a similar fashion for the secondary endpoints that are probability of experiencing an event including: any SELENA-SLEDAI\* flare by Week 60, any severe SELENA-SLEDAI\* flare by Week 60, any BILAG\* A flare by Week 60, a BILAG\* Renal A flare (for subjects with renal manifestations) by Week 60, and addition of aggressive adjunctive therapy to MMF or a change in MMF therapy to cytotoxic drug due to flare. These analyses will be conducted on the mITT and PP populations.

For the time to event endpoints (time to clinically significant disease reactivation, time to first SELENA-SLEDAI\* flare and time to first severe SELENA-SLEDAI\* flare), graphical summaries of time to event will be generated using Kaplan-Meier survival curves. The Greenwood method will be used to compute confidence intervals.

Descriptive statistics (mean, standard deviation or standard error, median, minimum, maximum and number of subjects in a group) and 95% confidence intervals will be reported for the difference between the treatment groups in cumulative steroid dose at Week 60; change in FACIT fatigue score from baseline to Weeks 24, 48, and 60; change in SF-36® PF and PCS domains from baseline to Weeks 24, 48, and 60; change in LupusQoL-US© from baseline to Weeks 24, 48, and 60, and change in SLICC/DI\* from baseline to Weeks 24, 48, and 60.

For subjects who meet the primary endpoint of clinically significant disease reactivation, the time to improvement in BILAG\* from maximum level during flare, time to recovery to BILAG\* C and time to return to pre-flare steroid dose will be analyzed using Kaplan-Meier curves. Descriptive statistics (mean, standard deviation or standard error, median, minimum, maximum) and 95% confidence intervals will be reported for the difference between the treatment groups in cumulative excess steroid dose from the time of clinically significant disease reactivation until return to pre-flare dose (or end of study participation). It is likely that some subjects will meet the primary endpoint close to the end of follow-up and will therefore be censored at the end of study follow-up for some or all of these endpoints. If one treatment group tends to flare earlier than the other does so that they are more likely to be censored, then censoring will be informative. Estimates of effect will therefore be biased.

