## 2.2 Secondary Objectives

### 2.2.1 Secondary Disease Activity Objectives

- To describe the effect of MMF withdrawal on measures of disease activity (including time to flare and severity of flare) in aggregate and in subgroups defined by demographics, disease manifestation (renal disease/extra-renal disease) and by baseline MMF dosing group (< 2000 mg per day / ≥ 2000 mg per day).
- To describe the effect of MMF withdrawal on damage accrual, needed medications, and subject quality of life.
- To describe the effect of MMF withdrawal on time to recovery from clinically significant disease reactivation and needed medications in the subgroup defined by disease reactivation during follow-up.

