# 7.3.13.1. Time from clinically significant disease reactivation to improvement in BILAG from maximum level during flare

**Endpoint:** See Section 7.2.1, *Computation of the Primary Endpoint*, for details on the definition of clinically significant SLE reactivation, and Section 7.3.4, *Probability of Experiencing a BILAG A Flare*, for more information on the BILAG and its scoring.

For each subject who experiences disease reactivation, time from clinically significant disease reactivation to improvement in BILAG from maximum level (at least an A or B) during the flare will be calculated in study days as: date of clinically significant disease reactivation – date of BILAG improvement. If multiple body systems have a BILAG flare at the visit, then the body system with the most severe score will be tracked for improvement; if multiple body systems have the same score (at least an A or B), then just one needs to show improvement.

Subjects who do not experience improvement in the BILAG prior to the end of their study participation or if the subject doesn't experience an increase in their BILAG score to a B or higher will be censored at their last visit date on study.

**Analysis**: Kaplan-Meier curves will be created for each treatment arm and will include 95% confidence intervals based on the Greenwood method.

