# 7.3.13.3. Cumulative excess systemic steroid dose from time of clinically significant disease reactivation to return to pre-flare dose or end of trial participation

**Endpoint:** See Section 7.2.1, *Computation of the Primary Endpoint*, for details on the definition of clinically significant SLE reactivation, and Section 7.3.8., *Systemic Steroid Dose*, for details on the definition of systemic steroids.

For each subject who experiences disease reactivation, excess systemic steroid dose will be summed from the time of clinically significant disease reactivation until the dose returns to pre-flare levels or the end of study participation, whichever occurs first. Excess systemic steroid dose will be defined as the total dose given for the flare – a subject's pre-flare steroid dose.

Version: 1.0 Page 28 of 48

Subjects who do not have an increase in their steroid use due to the flare will have their excess dose set to zero.

**Analysis**: Descriptive statistics (mean, standard deviation or standard error, median, minimum, maximum and number of subjects in a group) and 95% confidence intervals will be reported for the cumulative excess steroid dose in each treatment group.

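### Recovery is analysed only among subjects who reactivate, so by-arm results can mislead in either direction; separately, the protocol's censoring caveat names the wrong group

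*Protocol*

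**What the plan says.** Protocol 2.2.1 sets out to describe the effect of withdrawal on time to recovery and on needed "medications in the subgroup defined by disease reactivation during follow-up". Protocol 8.3.2.2 takes the same restricted set: "For subjects who meet the primary endpoint of clinically significant disease reactivation", Kaplan-Meier curves are planned for BILAG improvement, BILAG recovery and return to pre-flare steroid dose. A between-group difference with a 95% interval is planned for cumulative excess steroid dose.

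The SAP follows this in 7.3.13.1 ("For each subject who experiences disease reactivation, time from clinically significant disease reactivation to improvement in BILAG") and 7.3.13.3, where "excess systemic steroid dose will be summed from the time of clinically significant disease reactivation until the dose returns to pre-flare levels" or participation ends. Three scoring rules matter here:

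- In 7.3.13.1, a reactivated subject whose BILAG never rises to B or higher is censored at the last visit.
- In 7.3.13.2 and 7.3.13.4, subjects with no BILAG rise or no steroid rise are handled in the same way.
- In 7.3.13.3, a subject with no steroid rise is scored zero.

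On censoring, Protocol 8.3.2.2 first says: "It is likely that some subjects will meet the primary endpoint close to the end of follow-up and will therefore be censored". The next sentence begins: "If one treatment group tends to flare earlier than the other does so that they are more likely to be censored", and calls such censoring informative. It ends: "Estimates of effect will therefore be biased". No direction of bias and no remedy is given. SAP 7.3.13 does not repeat the caveat, and SAP Section 12 does not list it as a change.

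**The concern.** There are two separate problems.

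First, the two censoring sentences contradict each other. A reader who relies on the second will suspect the wrong arm.

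Second, reactivation is a post-randomization event, and Protocol 8.1 expects withdrawal to increase it. Reactivators on withdrawal are therefore a mixture: subjects who would have flared anyway and subjects who flared because MMF was stopped. Maintenance has only the first kind. A difference in recovery between these sets can arise although withdrawal changes nobody's recovery.

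This matters because Protocol 1.5 weighs withdrawal partly on whether the resulting flares are mild and easily treated, and these endpoints are the ones a reader would consult on that.

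**Working it through.** **Inputs from the documents.** Follow-up is fixed at 60 weeks (Protocol 3.2). There are 120 subjects, 1:1, so 60 per arm. Maintenance risk is 0.05 to 0.15 and the increase 0.05 to 0.15 (Protocol 8.1). The documents give no recovery times, so those below are assumptions, with exponential recovery.

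**Check of the planning inputs.** The criticised text contains no figure of its own. For Table 8.1 at risk 0.05, increase 0.05 and a = 0.15:
- SE = √(0.10×0.90/60 + 0.05×0.95/60) = 0.0479.
- Power = Φ(0.10/0.0479 − 1.036) = Φ(1.053) = 85.4%, against 85% stated.

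**1. Who is censored.** For a flare at week t and median recovery m, P(censored) = 2^(−(60−t)/m). A Week 16 flare leaves 44 weeks and a Week 48 flare leaves 12.

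| Assumed m (weeks) | Flare at Week 16 | Flare at Week 48 |
|---|---|---|
| 4 | <0.1% | 12.5% |
| 12 | 7.9% | 50% |
| 24 | 28% | 71% |

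The later flare is always the more censored.

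**2. What unequal timing does by itself.** Give both arms m = 12, with flares uniform over weeks 4–30 in one and 30–58 in the other. About 9% and 44% are censored, yet the Kaplan-Meier median is 12.0 weeks in both. Flare weeks accrued to study end, a proxy for cumulative excess dose, are 15.7 and 9.7. So timing leaves the curve alone but truncates the unadjusted sum in the later-flaring arm.

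**3. How different the two sets can be.** Assume everyone who would reactivate on maintenance would also do so on withdrawal. The share of withdrawal-arm reactivators with no maintenance counterpart is increase/(risk + increase). It runs from 0.05/0.20 = 25% to 0.15/0.20 = 75%.

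**4. Effect on the curves.** Take risks 0.10 and 0.20, so half of the withdrawal reactivators are added. Medians are 24 weeks (would flare anyway) and 8 weeks (added). Let q be the share of added flares that never reach BILAG B and are censored at Week 60. With x = 2^(−u/24), so that 2^(−u/8) = x³, the withdrawal curve is

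S(u) = ½x + ½[q + (1−q)x³].

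Setting S = ½ gives x + (1−q)x³ = 1 − q, and the median is u = 24·log₂(1/x).

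| q | x | Withdrawal median (weeks) | Maintenance median (weeks) |
|---|---|---|---|
| 0% | 0.682 | 13.2 | 24 |
| 25% | 0.593 | 18.1 | 24 |
| 50% | 0.453 | 27.4 | 24 |

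The medians are equal at x = 0.5: 0.5 + 0.125(1−q) = 1 − q, so q = 43%. With medians of 12 and 4 weeks everything halves: 6.6, 9.0 and 13.7 against 12. With added flares at 16 weeks and q = 0, the withdrawal median is 19.5 against 24.

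**5. The same scenario over all randomized subjects.** Flares are uniform over weeks 12–48, so remaining time L is uniform on 12–48. With θ = m/ln 2, mean unrecovered weeks per flare are θ[1 − (θ/36)(2^(−12/m) − 2^(−48/m))].
- m = 24: 34.6 × (1 − 0.440) = 19.4.
- m = 8: 11.5 × (1 − 0.108) = 10.3.
- Per randomized subject: maintenance 0.10 × 19.4 = 1.94 weeks; withdrawal 1.94 + 0.10 × 10.3 = 2.97 weeks.

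If the added flares are not milder, the medians among reactivators are both 24, while the all-subject figures are 1.94 and 3.88.

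**The case against.** Much can be said for the plan.

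- **Already descriptive.** All secondary analyses are labelled exploratory. SAP 7.3.13 plans separate curves by arm, without a test or hazard ratio, and SAP 7.3.13.3 reports excess dose within each group. Only Protocol 8.3.2.2 promises a between-group difference, and only for that endpoint. This stands in part: the exploratory label deals with multiplicity, not comparability, and the objective is still worded as an effect of withdrawal.
- **The subgroup is deliberate.** Protocol 2.2.1 restricts recovery to those who flare "in the subgroup defined by disease reactivation during follow-up". How long recovery takes after a flare is a fair clinical question, and an all-subject measure mixes incidence with duration. This stands: the all-subject measure belongs beside the curves, not in their place.
- **Steroid dose is largely covered.** SAP 7.3.9 already gives total and excess systemic steroid dose for every subject to Week 60 or early termination. This stands and narrows the gap to BILAG recovery and time above pre-flare dose.
- **Added flares may not be very mild.** Every reactivation requires a SELENA-SLEDAI flare plus increased treatment on a sustained basis, and Protocol 1.5 also says some flares could be severe. This stands, so the sizes above are illustrations only.
- **Few events.** SAP Section 12 reports 8 reactivations in the first 80 subjects, about 12 of 120 if that rate holds. Imprecision will be large. That is a further reason to discourage between-arm reading, not a defence of it.

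**Conclusion.** Both points hold as worded in the heading, as inexpensive corrections to secondary analyses. The primary analysis and Table 8.1 are unaffected.

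The censoring sentence is wrong whatever recovery time is assumed, because follow-up is fixed. The selection problem follows from the design. Its size and direction rest on assumed recovery times, on how mild the added flares are, and on how many miss BILAG B. In the illustration the withdrawal median is 13, 18 or 27 weeks against 24, with nobody's recovery altered.

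A reader might infer three stronger things that the documents do not support:

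- *The planned analysis will make withdrawal look as if it speeds recovery.* The BILAG rule in SAP 7.3.13.1 can reverse that; in the illustration it does so once 43% of added flares are censored.
- *The reversed word causes the misleading comparison.* It drives no calculation, and correcting it changes no estimate.
- *The protocol states the wrong direction of bias.* It states only which group is censored and that bias follows.

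**What to change.** 1. In Protocol 8.3.2.2, change *earlier* to *later*. Delete the statement that such censoring is informative, or limit it to the case where recovery time depends on flare date or flare type. Say instead that unequal timing truncates the cumulative excess dose.
2. In SAP 7.3.13, state that results among reactivators are not randomized comparisons and support no between-arm effect claim. Apply this also to the between-group excess-dose difference in Protocol 8.3.2.2.
3. Beside those results, add by-arm summaries over all mITT subjects: weeks from Day 0 to Week 60 in unrecovered reactivation (BILAG), and weeks above pre-flare steroid dose. Score zero for subjects who never reactivate. State how reactivators with no BILAG or steroid rise are scored, and how renal recovery is judged given that SAP 7.3.4 assigns no renal score at Day 0. Allow for dropout, for example with Aalen-Johansen state-occupancy estimates.
4. Cross-refer to SAP 7.3.9 for all-subject excess steroid dose.

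The cost is one corrected sentence, some SAP text and a few tables. BILAG is collected at every scheduled visit from baseline and medications at every visit (Protocol Table 6.1), so no new data are needed. The downside is a little more programming, and a measure that combines incidence with duration and so can only supplement the reactivator curves.
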